1.2.21 IPD Sharing Statement

IPD will be shared via the online EHS registry with contents adhering to their format. Accessible to all EHS members for all types of analyses. Currently shared: BEGZ, BEHA, BEHB, BEJR, BEJS, BEJT, BEJW, BEJX, BEJZ, BEKA, BEKB, BEKC, BEKG, BEKH, BEKI, BEKJ, BEKK, BEKL, BEKM, BELE, BELF, BELG, BELH, BELI, BELJ, BELK, BELL, BEOD, BETJ, BETK, BELN, BELO, BELQ, BELR, BELS, BELT, BELU, BELV, BELW, BELY, BEOF, BEOH, BEOO, BEPV, BEPX, BEPY, BEPZ, BEQA, BEQF, BEQG, BEQJ, BEQK, BEQQ, BEQR, BEQS, BEQT, BEQV, BEQX, BETN, BETO.

1.3 Protocol Version

Protocol version 3, December 26, 2022.

1.4 Funding

No finincial, material or other support.

2.1 Introduction

2.1.1 Background and Rationale:

Extended view totally extraperitoneal prosthesis (eTEP) repair is a fairly new, up-and-coming technique as a treatment option for ventral abdominal wall hernias. The endoscopic eTEP approach has been proven to be a feasible approach [4, 5]. Our center recently started offering this treatment option from September 7, 2021 (first performance of the eTEP surgery within our center) onwards as a minimally invasive alternative to an open Rives-Stoppa [6] repair. A quick search revealed some comparisons of eTEP with IPOM [7], or comparisons between robotic and endoscopic eTEP [8], but little or no information could be found about comparisons between endoscopic (non-robot-assisted) eTEP and open Rives-Stoppa repair. Since the endoscopic eTEP repair and the open Rives-Stoppa repair both consist of a retromuscular mesh placement, and the endoscopic eTEP procedure is offered as a minimally invasive alternative to an open Rives-Stoppa repair in our center, an objective comparison between the two of them seemed logical.

2.1.2 Objectives:

To compare the outcomes of endoscopic eTEP repair versus open Rives-Stoppa repair in terms of length of hospital stay, postoperative pain management and complications.

2.1.3 Trial Design:

Partially retrospective, partially prospective, two-group, parallel, observational, superiority cohort study with an allocation ratio of 1:1.

3.1 Methods: Participants, Interventions and Outcomes

3.1.1 Study setting

AZ Alma Eeklo, general hospital.

Country of data collection: Belgium.

3.1.2 Eligibility criteria

Inclusion and exclusion criteria for participants are listed under 1.2.10 and 1.2.11 respectively. AZ Alma Eeklo is the only eligible center. The eligible surgeons are those listed under 1.5 as contributor 2, contributor 3 and contributor 4.

3.1.3 Interventions

Explained under 1.2.9 and elaborated under 1.2.10, 1.2.11 and 1.2.12. All procedures were performed or will be performed by one of three surgeons listed under 1.5 as contributor 2, contributor 3 and contributor 4.

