1.2.12 Study Type

Single-center, observational study.

Non-randomized allocation:

- Group 1 (eTEP): First 30 patients who meet the inclusion criteria and do not exhibit any of the exclusion criteria will be investigated. The option for endoscopic eTEP repair, if feasible, is given preoperatively as a standard for the treatment of symptomatic midline abdominal wall hernias with concomitant rectus abdominis diastasis as an alternative to open Rives-Stoppa mesh repair. The modality of operative treatment is made in cooperation with the patient.
- Group 2 (Rives-Stoppa, control): Thirty patients will be selected out of all patients who underwent an open Rives-Stoppa (midline repair with sublay mesh) in our center and who do not meet any of the exclusion criteria. Patient selection will consist of matching to patients in group 1 according to gender and age (e.g. a male patient in group 1 will be matched to a male patient (group 2) out of our records

who underwent an open Rives-Stoppa repair and whose age most closely resembles the age of the matched patient in group 1).

Masking: None.

Assignment: Two-group, parallel.

Purpose: Comparing two routinely used interventions for the treatment of midline abdominal wall hernias with rectus abdominis diastasis.

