1.2.16 Primary Outcomes

- Outcome name: Length of hospital stay

Method of measurement: Time (days) spent within the hospital Timepoint: Start at day of operation (day zero) until day of discharge

Outcome name: Postoperative pain management

Method of measurement: Modality (type, generic name), duration (days), dosage (grams or

milligrams) and frequency (times per day) of analgesics administration

Timepoint: During hospital stay

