3.1.8 Methods: Assignment of interventions

Not applicable (not a controlled trial). No sequence generation, allocation concealment or blinding were applied. Matching of the control group is elaborated under 1.2.12. Participants are enrolled by one of three surgeons listed under 1.5 as contributor 2, 3 and 4. Matching of participants and (retrospective) creation of the control (Rives-Stoppa) group is done by contributor 1.

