4.1.4 Confidentiality

Uncoded data will only be accessible by the primary sponsor (1.2.2), which consists of the team of attending physicians. Only anonymised and relevant data will be available through the final manuscript and the EHS-registry as stated under 1.2.21. Data collection, management and monitoring are explained under 3.1.9 and 3.1.10.

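### Technique may be confounded with surgeon: three surgeons performed every procedure, but controls are matched on gender and age only

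*Protocol*

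**What the plan says.** Section 3.1.2 limits the operators: "The eligible surgeons are those listed under 1.5 as contributor 2, contributor 3 and contributor 4". Section 3.1.3 repeats this for all procedures, past and future, in either group: "All procedures were performed or will be performed by one of three surgeons listed under 1.5 as contributor 2, contributor 3 and contributor 4". Under section 3.1.8 the same people bring patients into the study: "Participants are enrolled by one of three surgeons listed under 1.5 as contributor 2, 3 and 4".

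Treatment is neither randomised nor masked. Section 1.2.12 says of the choice of operation: "The modality of operative treatment is made in cooperation with the patient". For the control group it says: "Patient selection will consist of matching to patients in group 1 according to gender and age". The example given there makes the rule definite: same gender, then the closest age among the centre's open Rives-Stoppa records. Surgeon plays no part in it.

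The two primary outcomes in section 1.2.16 are length of stay, measured as "Time (days) spent within the hospital", and the use of analgesics in hospital (type, duration, dosage and frequency). Section 2.1.1 dates the centre's first eTEP operation to September 7, 2021, and section 1.2.12 takes the first 30 eligible eTEP patients as group 1. Section 3.1.9 names software, Fisher's exact tests and Kaplan-Meier curves, and mentions no covariate.

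**The concern.** Length of stay and analgesic use are partly the result of decisions by clinicians who know which operation was done. Where practice differs between surgeons or their teams, the surgeon mix of a group affects its outcome. A technique introduced recently may be taken up faster by one surgeon than by the others, while the open controls come from the whole record of all three. Matching on gender and age does nothing to align the two mixes.

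If the mixes differ, a difference in practice between surgeons shows up as a difference between eTEP and Rives-Stoppa. Neither more patients nor closer age matching would remove it. Section 1.2.20 reports a longer median stay in the open group, and a reader cannot tell from the protocol whether surgeon contributes to that.

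**Working it through.** **What can be reproduced.** The only planning figure is 30 per group (section 1.2.14). No alpha, power, effect size or SD accompanies it, so it cannot be re-derived. For scale, with an assumed two-sided alpha of 0.05 and 80% power, 30 per group detects (1.960 + 0.842) x sqrt(2/30) = 0.72 SD. Power for 0.5 SD is 49%.

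**Inputs from the protocol.** Three surgeons, all eligible for both groups (3.1.2, 3.1.3); matching on gender and age (1.2.12); 30 per group (1.2.14).

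**Inputs that the protocol does not give.** The share of each technique done by each surgeon, the difference in outcome between surgeons, and the SD of length of stay. All three are assumed below.

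**Formula.** For any number of surgeons, bias = the sum over surgeons of (share of group 1 - share of group 2) x that surgeon's mean outcome. In the simple case where one surgeon differs from the other two, this becomes:

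bias = (difference between groups in that surgeon's share) x (surgeon effect)

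The bias is zero if either factor is zero.

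**False-positive rate.** With outcomes in SD units, the standard error of a difference in means is sqrt(2/30) = 0.258. A two-sided normal test at 5% then rejects with probability Phi(b/0.258 - 1.96) + Phi(-b/0.258 - 1.96), where b is the bias. The small addition to the variance from mixing surgeons is ignored.

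| Difference in share | Effect 0.25 SD | Effect 0.5 SD | Effect 1.0 SD |
|---|---|---|---|
| 0 | 5.0% | 5.0% | 5.0% |
| 0.25 | 5.7% | 7.7% | 16.2% |
| 0.50 | 7.7% | 16.2% | 49.1% |
| 1.00 (full separation) | 16.2% | 49.1% | 97.2% |

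One cell in full: 0.50 x 0.5 SD = 0.25 SD; 0.25/0.258 = 0.97; rejection 16.2%.

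**In days.** Assume shares differing by 0.3 to 0.7, surgeons differing by 0.5 to 1 day, and an SD of 2 days. The bias runs from 0.3 x 0.5 = 0.15 day to 0.7 x 1.0 = 0.70 day, or 0.075 to 0.35 SD. A t test with 58 degrees of freedom and noncentrality d x sqrt(15) (0.29 to 1.36) rejects in 5.9% to 26.6% of studies. This range leaves out equal shares, which the protocol equally allows and which give 5%.

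**Limits.** A test on means is used only to show scale; section 1.2.20 reports medians. The results run from no harm to severe harm, and the unreported split by surgeon largely decides where the study falls.

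**The case against.** - **Confounding is not shown.** A reader might infer that technique is confounded with surgeon. The protocol does not support that. The same three surgeons are eligible for both groups, and no section gives procedures by surgeon and technique. If each did similar shares of both operations, this confounding is absent. The objection stands, and the point is limited to a possibility.
- **Who decides discharge and analgesia is not stated.** A reader might also infer that the three surgeons control both primary outcomes. Section 4.1.4 says only of the sponsor "which consists of the team of attending physicians". That fits shared postoperative care as well as individual habits. This stands too.
- **One centre and a fixed team of three already limit variation between operators.** True, but this restricts who operates; it does not balance the groups.
- **The analysis may be specified elsewhere.** Section 3.1.9 lists tools rather than a full analysis, and a statistical analysis plan that is not shown may adjust for surgeon. Its silence is therefore no fault. The control-selection rule is different: section 1.2.12 sets it out in full, and an analysis plan does not change who was selected.
- **The magnitude is hypothetical.** It is. No input to the bias comes from the protocol except the group size.
- **Re-matching now would mean choosing controls again after results are known.** This stands, and it shapes the remedy.

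**Conclusion.** The point holds as a potential confounder left uncontrolled by the selection rule. Surgeon is identifiable for every case, the comparison is unmasked and not randomised, and the rule in section 1.2.12 leaves the surgeon mix to chance and to the pattern of eTEP uptake. Whether the mixes differ, and whether practice differs between surgeons, cannot be learned from the protocol. The bias may be zero. Under moderate assumptions (share difference 0.25 to 0.50, surgeon effect 0.5 SD) the false-positive rate would be 7.7% to 16.2% instead of 5%; near-complete separation would be much worse. The point does not show that the reported differences are wrong. It is worth acting on because the missing information can be tabulated cheaply.

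**What to change.** **Rule in section 1.2.12, as it should read for a study of this design.** Among controls of the same gender within a stated age limit, take one operated on by the same surgeon where available; otherwise take the nearest in age. The age limit must be written down so that the choice remains determinate.

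**Practical form now.** Recruitment is complete (section 1.2.15) and a results summary is posted (section 1.2.20), so keep the existing controls and:

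1. Show a table of surgeon by group for all 60 participants.
2. Add a sensitivity analysis of length of stay, stratified by or adjusted for surgeon as a three-level factor.
3. Do the same for one defined analgesia measure. The outcome headed "Outcome name: Postoperative pain management" has several components and no single summary, so one must be named. The amount per day by category, already defined in section 1.2.20, would serve if one category is chosen.
4. Label these analyses as added after the results were known, unless an analysis plan already contains them.
5. If surgeons hardly overlap between techniques, state that the comparison is of technique together with surgeon.

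**Cost.** One table from the operating records and two degrees of freedom in an adjusted model. The adjusted interval will be wider, and with little overlap there is no usable within-surgeon estimate. The matching rule, if used, would give somewhat looser age matches.

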3.1.4 Outcomes

Primary and secondary outcomes are listed under 1.2.16 and 1.2.17 respectively.

3.1.5 Participant timeline

See "Participant flow" under 1.2.20.

3.1.6 Sample size

Explained under 1.2.14.

3.1.7 Recruitment

No specific recruitment measures are undertaken. Participants are recruited retrospectively post-surgery, or, if possible at consultation when they present with eligible pathology and inclusion criteria. No difference to normal standard of care is made. From September 2021 onwards, the eTEP procedure was offered as an alternative to open Rives-Stoppa mesh repair for eligible participants.

3.1.8 Methods: Assignment of interventions

Not applicable (not a controlled trial). No sequence generation, allocation concealment or blinding were applied. Matching of the control group is elaborated under 1.2.12. Participants are enrolled by one of three surgeons listed under 1.5 as contributor 2, 3 and 4. Matching of participants and (retrospective) creation of the control (Rives-Stoppa) group is done by contributor 1.

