0.1 Protocol additions

Version 2:

- Addition to participant flow (1.2.20)
- Completion of entry to ClinicalTrials.gov.

Version 3: Last updated December 26, 2022

- Addition of ClinicalTrials.gov ID (1.1)
- Addition to 'actual sample size' (1.2.14)
- Addition to 'recruitment status' (1.2.15)
- Addition of completion date (1.2.19)
- Addition to participant flow and flowchart (1.2.20)
- Additional registration to EHS-registry with addition to 'baseline characteristics' (1.2.20)
- Correction of 'adverse events' under 1.2.20 since participant previously denoted with an adverse event exhibited exclusion criteria and was not included
- Addition of 'adverse events' (1.2.20)
- Addition of 'brief summary' (1.2.20)
- Addition of 'date of posting of results summaries' (1.2.20)
- Addition to IPD sharing statement (1.2.21)
- Addition to 'contributions' (1.5)
- Addition to 'statistical analysis' (3.1.9)

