3.1.9 Methods: Data collection, management, and analysis

Data collection is done by reviewing the electronic medical records of participants. No additional tests or interventions are undertaken other to those that are considered as standard of care. Collected data can be found in the EHS-registry as mentioned under 1.2.20 and 1.2.21. Additional data (if applicable) will be supplied within the final report. All relevant data regarding the outcome measures explained under 1.2.16 and 1.2.17 will be collected for all enrolled participants.

Uncoded data is entered and stored to files only accessible to members of the primary sponsor (1.2.2). Data quality will be regularly checked by contributor 1.

A biostatistician was consulted for advice regarding statistical analysis. Statistical analysis was performed by contributor 1. JASP [9] was used for the majority of statistical analysis, Vassarstats [10] was used to calculate Fisher's exact tests on 3 x 2 contingency tables, XLSTAT [11] was used to create Kaplan-Meier curves.

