4.1.8 Dissemination policy

The primary sponsor and investigators/contributors plan to publish the results to a medical journal (title to be discussed). Data will also be available at the EHS-registry (see 1.2.20, 1.2.21, 4.1.4 and 4.1.6).

All authors contributed to the study conception and design. Material preparation, data collection and analysis were performed by contributor 1 (see 1.5). The first draft of the manuscript will be written by contributor 1 and all authors/contributors will comment on previous versions of the manuscript. All authors/contributors will read and approve of the final manuscript. No intended use of professional writers.

If allowed by the accepting journal, the study protocol will be made publicly available. Participant level dataset will be available (anonymized) at the EHS-registry as stated above. Statistical code is discussed under 3.1.9.

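### One unmasked person picks the Rives-Stoppa controls from records that can already hold the outcomes, then extracts and analyses those outcomes, under a matching rule with no outcome-blind step or tie-break

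*Protocol*

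**What the plan says.** The protocol spreads the relevant roles over several sections.

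- **Control group.** Section 3.1.8: "Matching of participants and (retrospective) creation of the control (Rives-Stoppa) group is done by contributor 1".
- **Enrolment.** Also 3.1.8: "Participants are enrolled by one of three surgeons listed under 1.5 as contributor 2, 3 and 4".
- **Data and analysis.** Section 4.1.8: "Material preparation, data collection and analysis were performed by contributor 1". Section 3.1.9 adds "Statistical analysis was performed by contributor 1" and "Data quality will be regularly checked by contributor 1". A biostatistician was consulted for advice only. Outcome data come from the electronic medical records.
- **Masking.** None, according to 1.2.12 and again 3.1.8.
- **Matching rule.** Section 1.2.12 draws each control from the centre's records of open Rives-Stoppa repairs: same gender, and the patient "whose age most closely resembles the age of the matched patient in group 1".
- **A late exclusion.** The version 3 log in 0.1 explains a correction to the adverse-event list: a "participant previously denoted with an adverse event exhibited exclusion criteria and was not included".

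**The concern.** When controls are picked from past operations, length of stay and in-hospital analgesia (the two primary outcomes in 1.2.16) can already be in the file that is opened to check eligibility and age. Complications can be there too. If the selection rule leaves a choice, whoever makes it can know how each candidate fared. The same person then extracts and analyses the data, so no second, independent view would reveal an uneven choice.

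At stake is the composition of Group 2 in a study that 2.1.3 describes as a superiority comparison, with neither randomisation nor masking to fall back on. The late exclusion raises a related question: were records with an event examined for eligibility more closely than records without one? If so, complications would be removed selectively.

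**Working it through.** The protocol gives no figure on this point to reproduce. The check traces roles and timing, then asks how much choice the rule leaves and how much one choice can matter.

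**1. Roles.** Contributor 1 matches and builds Group 2 (3.1.8), collects the data (4.1.8), checks their quality and runs the statistics (3.1.9). Contributors 2 to 4 enrol (3.1.8). The overlap of selection, extraction and analysis is therefore documented for the control group. It is not documented for eTEP eligibility.

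**2. Timing.** Section 3.1.8 calls the creation of the control group retrospective. The flow table in 1.2.20 shows 23 of 30 per group (23/30 = 76.7%) on June 9, 2022, the day of ethics approval, and 7/30 = 23.3% later. Both groups have the same count at every date, which fits controls being added as eTEP patients were added. No section places a step between selecting a control and seeing that patient's outcomes.

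**3. What the rule fixes.** It fixes gender and nearest age. It does not fix the unit of age, what happens when two candidates are equally near, the order in which eTEP patients are matched, or the calendar period of the pool. Selecting thirty patients suggests that no control is used twice, but this is not stated as a rule.

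**4. How often the nearest age is tied.** The pool size and age distribution are not given, so these are assumptions: 30 sequential matches within gender, without replacement, age SD about 12.5 years, even gender split. Mean number of tied choices out of 30, by simulation:

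| Assumed pool | Age in whole years | Age in days |
|---|---|---|
| 60 | about 11 | about 0.05 |
| 100 | about 15 | about 0.1 |
| 200 | about 21 | about 0.2 |

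The unit of age drives the answer far more than the pool size, and the protocol does not state it.

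**5. What one participant can move.** This is an illustration from the counts in 1.2.20, assuming at most one event per participant (not stated). Post-discharge Clavien-Dindo IIIa or higher is 2 + 1 = 3 of 30 for eTEP and 5 + 4 = 9 of 30 for open repair; two-sided Fisher p = 0.104. Replacing one control gives 3/30 vs 8/30 (p = 0.181) or 3/30 vs 10/30 (p = 0.058). Two replacements in the same direction give 3/30 vs 11/30 (p = 0.030).

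**6. The removed participant.** Suppose that person would have been a 31st member of a group with k events. Removal changes the rate by k/31 − (k − 1)/30 = (31 − k)/930. For k = 1 this is 30/930 = 3.2 percentage points; for k = 13 (the in-hospital eTEP total of 1 + 12) it is 18/930 = 1.9 points.

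**The case against.** Much limits the room for choice. The eTEP group is the first thirty eligible patients, and some may be enrolled at consultation before surgery (3.1.7). The control rule is stated in advance. The control exclusions in 1.2.11 (transverse abdominis release, anterior component separation, inguinal repair) are recorded operative facts with little scope for interpretation. If age was compared by date of birth, ties hardly arise. A small unfunded cohort may have one person for all these tasks, and the protocol says so openly. Tie-breaks are also often left to an analysis plan.

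Most of this stands, and it rules out three stronger readings that a reader might infer:

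- **That contributor 1 decides all eligibility.** Section 3.1.8 assigns enrolment to the three surgeons. They are unmasked as well, but they are not described as extracting or analysing outcomes.
- **That a large part of Group 2 was chosen at will.** This needs ages in whole years, which the protocol does not state. A tie would not show that outcomes guided the choice either.
- **That the adverse event prompted the exclusion.** The log shows only that the person was listed with an event and was then recorded as meeting exclusion criteria. Applying 1.2.11 is what the protocol requires. The participant flowchart is not shown and may account for the case.

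The objection does not supply a safeguard. How controls are chosen, and by whom, is a design matter that the protocol itself sets in 1.2.12 and 3.1.8. Neither section separates selection from outcomes or makes the choice unique.

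**Conclusion.** The point holds for the control group: selection, extraction and analysis lie with one unmasked person, and the rule neither hides outcomes nor determines the choice fully. This is an unguarded route to bias, not evidence of bias.

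Its size cannot be fixed from the protocol. Under the assumed pools of 60 to 200, discretion from ties ranges from almost none (age in days) to about 11 to 21 of 30 matches (age in whole years). Matching order and calendar period add an amount that cannot be calculated here. With 30 per group, one or two changed controls can alter how a complication comparison reads, on the one-event-per-participant assumption. The effect on stay and analgesia cannot be computed without individual data.

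The late exclusion is a reporting gap. The text shown does not give the group or the criterion, or say whether event-free participants were re-checked. The safeguard is cheap and still possible, so the change is worth making.

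**What to change.** **In 1.2.12 and 3.1.8:**

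- Select controls from a list that holds only sex, date of birth, operation date and the procedures performed at the index operation. State the range of operation dates covered.
- Apply 1.2.11 to every listed case. All Group 2 exclusions are intraoperative, so this list is enough for them.
- Match on nearest age, computed from date of birth, without replacement and in a fixed order (for example by eTEP operation date). Break ties by nearest operation date.
- Freeze the list of controls before outcomes are extracted.
- State who rules on eligibility in each group.

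**For the completed data:**

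- Re-run this match. Once the list is complete the rule leaves no choice, so knowledge of outcomes can no longer steer it. Report how many of the 30 controls change and whether the results change.
- Re-check all 60 participants against 1.2.11 regardless of events. For eTEP this also needs the preoperative hernia and diastasis findings.
- Report the removed participant's group, event and exclusion criterion.

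**Cost:** a few hours on existing records and some protocol wording. The downside is that outcomes must be extracted for any replacement controls.
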